#### 5.4.2 Geometric Mean Fold Rise

The geometric mean fold rise (GMFR) is given by taking the mean of the natural logarithm of the fold increases (Section 5.3.2.2). Therefore, for the fold increases  $fi_1, \dots, fi_n$ , the GMFR is

$$GMFR = \exp \sum_{j=1}^n (\ln\{fi_j\}/n).$$

Which is equivalent to

$$GMFR = \frac{GM_3}{GM_1}$$

where  $GM_1$  is the geometric mean at Visit 1 and  $GM_3$  is the geometric mean at Visit 3.

The 95% confidence interval for GMFR will be calculated using the same method as the 95% CI for GM (outlined in Section 5.4.1) but using the log of the fold rises rather than the log of concentrations.

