## **5.3.2 Immunogenicity**

### **5.3.2.1 Fold Increase**

The fold increase is calculated by taking the ratio of assessments from two visits, which for this study will be Visit 1 (Day 1) and Visit 3 (Day 29) assessments.

If  $v_1$  is a subject's Visit 1 record and  $v_3$  is a subject's Visit 3 record then the fold increase is:

$$fi = \frac{v_3}{v_1}.$$

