## 5.4 Statistical Analysis Methods

### 5.4.1 Geometric Mean

The geometric mean (GM) of a set of numbers  $x_1, x_2, \dots, x_N$  is calculated by taking the exponential of the mean of the logged values, as per the following formula:

$$GM_x = \exp \left\{ \frac{\sum_{i=1}^N \ln(x_i)}{N} \right\}.$$

The geometric standard deviation (GSD) for the same set of numbers is given by

$$GSD_x = \exp \left\{ \sqrt{\frac{\sum_{i=1}^n \left( \ln \left( \frac{x_i}{GM_x} \right) \right)^2}{n}} \right\}.$$

The 95% confidence interval (CI) is calculated as per the following formula:

$$95\% CI = \exp \left\{ \ln(GM) \pm Z_{1-\frac{\alpha}{2}} \frac{\ln(GSD)}{\sqrt{n}} \right\}$$

where  $\alpha$  is the selected level of confidence. All confidence intervals outlined in this SAP will be two sided 95% confidence intervals, i.e. with  $\alpha = 0.05$ .

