## 6 Sample Size

A sample size of 80 subjects will provide sufficient serum for the establishment of proficiency panels to confirm assay validation of the validated serology assays planned to support the clinical development plan for HIL-214.

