### **9.1 Main Analytical Approach**

For all immunogenicity variables a standard summary of the number of subjects with an assessment (n), mean, standard deviation, median, Q1, Q3, minimum and maximum will be presented alongside the number of assessments below the LLOQ and LLOD and above the ULOQ. The number of subjects that are missing an assessment will also be summarized.

As well as the standard continuous summary of the outcomes, geometric mean titers (GMTs), geometric mean fold rise (GMFR) and seroresponse rate (SRR) will be presented (as defined in **Sections 5.3.2 and 5.4**) for each immunogenicity variable. The 95% confidence intervals (CI) for GM, GMFR and SRR as well as geometric standard deviation (GSD) will also be provided.

In addition, for each immunogenicity variable a reverse cumulative distribution curve will be produced, with titer on the x-axis and the percentage of subjects below the titer value on the y-axis.

Line graphs and boxplots summarizing the GMT for each trial vaccine group for the serotypes GI.1 and GII.4 will also be produced. These outputs will both have the visits of baseline (Day 1) and Visit 3 (Day 29) on the x-axis and the GMT on the y-axis, presenting data on the log scale.

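### SAP 5.4.2 equates the paired GMFR with the ratio of the two visit GMTs without the condition that both means use the same subjects

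*SAP*

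**What the plan says.** SAP 5.3.2.1 states: "The fold increase is calculated by taking the ratio of assessments from two visits". The two values are one subject's Visit 1 and Visit 3 records, so a fold increase exists only for a subject who has both.

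SAP 5.4.2 builds on this: "The geometric mean fold rise (GMFR) is given by taking the mean of the natural logarithm of the fold increases", and the displayed formula exponentiates that mean. The next line reads "Which is equivalent to" and gives GM3/GM1. The only description of the terms is that GM1 "is the geometric mean at Visit 1 and" GM3 is the one at Visit 3. The interval follows the method of SAP 5.4.1, "but using the log of the fold rises rather than the log of concentrations".

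The parts of the plan that could have supplied a same-subjects condition do not:

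- SAP 9 runs the immunogenicity analyses on the Safety and Per Protocol sets. By SAP 7.1 the Safety set is everyone dosed, and neither set requires both titers. A missing sample is not among the examples of major deviations, although that list is open-ended.
- SAP 9.1 summarises each variable on subjects with an assessment and adds: "The number of subjects that are missing an assessment will also be summarized".
- SAP 7.3 deals with partial dates and times and has no rule for missing titers.

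**The concern.** GMFR is one of three statistics named for the primary analysis in Protocol 13.1.3, and it is reported for two assays and two antigens. A reader who takes the equivalence at face value may divide the GMTs already tabulated by visit. Those GMTs are naturally computed on whoever has a result at each visit.

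The documents show how the two groups can come apart. Protocol 2.2, note (h), has blood taken from all subjects before vaccination on Day 1. Protocol 7.4 ends all procedures and data collection at early termination. A dosed subject who leaves before Day 29 therefore counts in GM1 but not in GM3, and has no fold increase. Any baseline difference between such subjects and the rest would pass into the ratio. The interval would still be paired, so estimate and interval would describe different subjects. The SRR needs a fold increase and is therefore also paired, so it could stand beside a GMFR with a different and unstated denominator.

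**Working it through.** **Inputs.** The two formulas and the interval rule come from SAP 5.4.2, and the fold increase from SAP 5.3.2.1. The planned N of 80 is from SAP 6. SAP 5.4.1 sets the level: "All confidence intervals outlined in this SAP will be two sided 95% confidence intervals". The documents give no missingness rate, no titer SD and no baseline contrast; every value used for these below is an assumption.

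**1. The plan's identity with complete pairs.** For the same n subjects, mean(ln v3 − ln v1) = mean(ln v3) − mean(ln v1). Exponentiating gives GMFR = GM3/GM1 exactly. In one simulated data set of 80 complete pairs both forms gave 7.3602. The SAP's statement is reproduced in this case.

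**2. Some Day 29 results missing.** Let m be the fraction of subjects with Day 1 only, and r the baseline GMT of those subjects divided by that of the complete subjects.

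- ln GMFR (paired) = mean ln v3 in complete subjects − mean ln v1 in complete subjects.
- ln(GM3/GM1) = mean ln v3 in complete subjects − [(1 − m) × mean ln v1 in complete subjects + m × mean ln v1 in missing subjects].
- The second minus the first = m × (mean ln v1 in complete − mean ln v1 in missing) = −m ln r.

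So ratio form ÷ paired GMFR = r^(-m). It equals 1 when m = 0, or when r happens to be 1. A numerical check with 8 of 80 missing gave 0.05755 on both sides of the log identity.

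**3. A small example.** Day 1 titers are 10, 20, 40 and 640; Day 29 titers are 80, 160, 320 and missing.

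- Paired GMFR: each complete subject rises 8-fold, so 8.00.
- Ratio on all available data: GM3 = 160; GM1 = (10 × 20 × 40 × 640)^(1/4) = 47.57; ratio = 3.36.
- By the formula: r = 640/20 = 32 and m = 1/4, so 8 × 32^(-0.25) = 3.36.
- Ratio restricted to the three complete subjects: 160/20 = 8.00.

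The contrast is deliberately extreme. It shows the mechanism, not a likely size.

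**4. Assumed values for this trial** (ratio form ÷ paired GMFR):

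| Missing at Day 29 | r = 2 | r = 4 | r = 1/2 |
|---|---|---|---|
| 1 of 80 (1.25%) | 0.991 | 0.983 | 1.009 |
| 4 of 80 (5%) | 0.966 | 0.933 | 1.035 |
| 8 of 80 (10%) | 0.933 | 0.871 | 1.072 |

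With r = 2 the understatement is 3.4% at 5% missing and 6.7% at 10%. With r = 4 it is 6.7% and 12.9%. If the missing subjects have lower baselines, the ratio overstates instead.

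**5. Scale.** If 8 of 80 are missing completely at random and the ln-titer SD is 0.8 to 1.6 (assumed), the gap between the forms has a one-SD factor of exp(SD × √(8/(80 × 72))) = 1.03 to 1.06. The 95% half-width factor for a GMFR on 72 pairs, with an ln-fold SD of 0.8 to 1.6 (assumed), is exp(1.96 × SD/√72) = 1.20 to 1.45. At the values used here, the gap is smaller than the sampling uncertainty already in the interval.

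**The case against.** The best defence is that the SAP's operative definition is already paired. The equivalence follows directly from a sum over n fold increases and can be read as an algebraic remark about those same n subjects, for whom it is exact. SAP 5.4.1 defines a geometric mean for a given set of numbers, and the natural set here is those subjects. The interval needs the mean log fold rise at its centre, so a programmer who computes the interval already holds the paired estimate. The SRR uses the same fold increase, and SAP 8 bases percentages on non-missing observations. SAP 9.1 also asks for the number assessed and the number missing.

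Nothing in the trial turns on a few percent, either. The primary analysis is descriptive and single-arm, with no test or threshold, and the size was set by material rather than precision: "A sample size of 80 subjects will provide sufficient serum". The documents give no reason why healthy adults would leave within four weeks in a way related to baseline norovirus titer.

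Most of this stands and limits the weight of the point. It does not remove it. GM1 and GM3 are described only by visit, no other section confines them to pairs, and the count of pairs is not requested. A reader might go further and infer that the reported GMFR will mix different subjects. The documents do not support that, because the leading definition and the interval are both paired.

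**Conclusion.** The unconditional equivalence in SAP 5.4.2 is incorrect as written: it is guaranteed only when both geometric means come from the same subjects. The paired definition and the paired interval are correct. This is a minor specification error, and it has an effect only if the ratio form is programmed and some subjects lack one of the two results.

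In that case the discrepancy is the factor r^(-m). For m of 5% to 10% and r = 2 that is a 3% to 7% understatement, and with complete pairs it is zero. These figures rest wholly on assumed missingness and an assumed baseline contrast, and they should not be read as a forecast of bias. The larger value of 12.9% needs both 10% missing and a four-fold higher baseline in the missing subjects, which nothing in the documents suggests. The derivation covers results missing at Day 29, the route the documents describe; a missing Day 1 result would add a similar term. No stated conclusion of the trial depends on the outcome.

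**What to change.** Keep the exponentiated mean of the within-subject log fold increases as the only definition of GMFR in SAP 5.4.2. Either delete the equivalence, or add after it: where GM1 and GM3 are computed only in subjects with both a Visit 1 and a Visit 3 result. Compute the estimate and its interval from the same pairs, and show the number of pairs beside GMFR and SRR for each assay and antigen, separately from the by-visit n for the GMTs. In the same edit, correct the cross-reference in 5.4.2: fold increases are defined in 5.3.2.1, not 5.3.2.2.

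The cost is one sentence in the SAP and one column in the table shell. It needs no protocol amendment and no new data.

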## 6 Sample Size

A sample size of 80 subjects will provide sufficient serum for the establishment of proficiency panels to confirm assay validation of the validated serology assays planned to support the clinical development plan for HIL-214.

## 7 General Considerations

### 7.1 Analysis Sets

For the purposes of analysis, the following subject analysis sets are defined in Table 2:

**Table 2: Subject Analysis Sets**

Subject Analysis Set	Description
Enrolled analysis set	

All subjects who signed the informed consent form.

Safety analysis set	

All subjects who received HIL-214.

Per protocol analysis set	

All subjects who received HIL-214 and did not have any major protocol deviations that impact immunogenicity

Protocol deviations will be logged within the clinical trial management system and categorized as important/not important, with important protocol deviations being categorized as major/not major.

Important protocol deviations are a subset of protocol deviations that might significantly affect the completeness, accuracy, and/or the reliability of the study data or that might significantly affect a subject's rights, safety, or well-being.

Major protocol deviations are a subset of important protocol deviations that might significantly impact the immunogenicity analysis.

Major protocol deviations may include, but are not limited to:

- Fraudulent data
- Inclusion/exclusion criteria not being met but the subject was dosed
- Visit 2 or Visit 3 occurred out of window
- Study treatment impacted by a temperature excursion
- Vaccine administered or blood sample collected while one of the delaying criteria met
- Incorrect volume of IP administered
- IP stored outside of temperature range
- Participant dosed with expired IP

The classification of a major protocol deviation will take place prior to database lock and any subjects deemed to have a major protocol deviation will be excluded from the Per Protocol set.

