## 5 Study Methods

### 5.1 General Study Design and Plan

[figure not shown]
This is a phase 2, single-arm, open-label trial for serologic assay validation, proficiency testing, safety and immunogenicity of HIL-214, in healthy adults aged 18 to 49 years. Vaccination with a single dose of HIL-214 will occur on Day 1.

As shown in **Figure 1**, the study comprises of 3 scheduled site visits (Day 1, Day 8, and Day 29) and one telephone contact (Day 85). Visits 1, 2, and 3 involve blood draws. **Table 1** shows the visit windows for Visits 2 and 3.

The final contact to collect safety data is scheduled on Day 85.

Throughout this document, trial vaccine will refer to the investigational vaccine administration of HIL-214.

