## **9 Immunogenicity Analysis**

The primary endpoint will consider the immunogenicity of HIL-214 at Visit 3 (Day 29) and all analysis will be defined in this section. Analyses will be completed for the safety analysis set and per protocol analysis set. Subjects with immunogenicity samples taken outside of the visit windows (as described in **Table 1**) will not be included in analyses which use the per protocol analysis set.

The immunogenicity variables, HBGA-blocking titers and total immunoglobulin (pan-Ig) titers that are specific for GI.1 VLP and GII.4c VLP will be summarized. Along with the following summaries, the immunogenicity data will be listed by subject.

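### Minor: an out-of-window Day 8 visit is listed as a possible major deviation, so it can drop a valid Day 1/Day 29 titer pair from the supportive per-protocol analysis

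*SAP*

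**What the plan says.** SAP 7.1 sets a test and then gives examples. The test is: "Major protocol deviations are a subset of important protocol deviations that might significantly impact the immunogenicity analysis". The examples are introduced by "Major protocol deviations may include, but are not limited to", and one of them is "Visit 2 or Visit 3 occurred out of window". The consequence is that "any subjects deemed to have a major protocol deviation will be excluded from the Per Protocol set", with classification made before database lock. SAP Table 2 and protocol 13.1.1 define the set in the same terms: vaccinated subjects with no major deviation that affects immunogenicity.

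SAP 9 adds a second rule without a discretionary step. "Subjects with immunogenicity samples taken outside of the visit windows" of Table 1 are left out of the per-protocol analyses. Table 1, according to SAP 5.1, "shows the visit windows for Visits 2 and 3": +2 days for Day 8 and +3 days for Day 29, with no minus side.

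**The concern.** The Visit 2 trigger concerns a visit that supplies no data to the analysis the set is meant to support. Exclusion is by subject, so a Day 8 visit on the wrong date could remove a correctly timed Day 1/Day 29 pair, with no gain in validity for those titers. Because the Day 8 window is one-sided (Days 8 to 10), a visit one day early already counts as out of window.

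SAP 9 leaves a further ambiguity. Its sentence most naturally means Day 29 samples, but it points to a table that also lists Day 8, and protocol 9.3.4 describes the blood taken at both visits as being for immunogenicity testing. A literal reader could treat exclusion for a mistimed Day 8 sample as compulsory. At stake are some precision in, and consistent membership of, a supportive analysis.

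**Working it through.** **Does any titer analysis in this SAP use Day 8?**

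- Primary endpoints (protocol 5.2, SAP 4.2): HBGA-blocking and pan-Ig titers at Day 1 and Day 29.
- Fold increase (SAP 5.3.2.1): the ratio of Visit 3 to Visit 1. Seroresponse (5.3.2.2) and GMFR (5.4.2) derive from it.
- Line graphs and boxplots (SAP 9.1): "These outputs will both have the visits of baseline (Day 1) and Visit 3 (Day 29) on the x-axis".
- Blood table (protocol 9.1.6, Table 9.a): the serum row has 100 mL on Day 1, none on Day 8 and 100 mL on Day 29.
- Exploratory endpoints (SAP 4.1): documented outside this SAP.
- Dosing (protocol 8.4): a single dose on Day 1, so Day 8 timing cannot change exposure.

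None uses Day 8, so an isolated Visit 2 miss cannot affect a Day 1/Day 29 pair.

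**How likely is at least one such miss?** The documents give no rate. With an assumed independent probability q per subject, the chance is 1 − (1 − q)^80. For q = 2% this is 80%, and for q = 5% it is 98%.

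**What would the exclusions cost?** The documents give no per-protocol precision figure to reproduce; N = 80 rests on serum volume (SAP 6). By SAP 5.4.1 the log-scale half-width is Z(0.975) × ln(GSD)/√n. For a given GSD, the relative widening is therefore √(80/n) − 1. The SRR interval is exact Clopper-Pearson (SAP 5.3.2.2). The numbers lost and the SRRs below are assumptions.

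| Lost | n | GMT/GMFR log-CI widening | SRR CI width, SRR near 60% | SRR CI width, SRR near 80% |
|---|---|---|---|---|
| 0 | 80 | – | 48/80: 22.36 points | 64/80: 18.55 points |
| 1 | 79 | 0.63% | 47/79: 22.55 | 63/79: 18.75 |
| 4 (5%) | 76 | 2.60% | 46/76: 22.91 | 61/76: 18.97 |
| 8 (10%) | 72 | 5.41% | 43/72: 23.62 | 58/72: 19.41 |
| 12 (15%) | 68 | 8.47% | 41/68: 24.27 | 54/68: 20.39 |

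The largest gains in SRR width are 24.27 − 22.36 = 1.91 points and 20.39 − 18.55 = 1.84 points. The second depends partly on the count chosen: 55/68 gives 19.88, a gain of 1.33.

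On the titer scale, the multiplier exp(1.96 s/√n) with an assumed ln-titer SD of s = 1.0 goes from 1.245 at n = 80 to 1.268 at n = 68. With s = 1.5 it goes from 1.389 to 1.428.

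**The case against.** The strongest reply is that the SAP already contains the safeguard. A deviation must be important, must be one that might significantly affect the immunogenicity analysis, and must be judged so before lock. If Day 8 timing cannot touch the titers, a correct application of that test keeps the subject in. This stands as far as it goes: exclusion is not automatic. But Visit 2 is named expressly as an example, and nothing tells the data review meeting (SAP 8.2) to set it aside for the titers. An example that cannot meet its own definition invites inconsistent classification.

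Secondly, the purpose of the 30 mL Day 8 draw is redacted, and one common set for all immunogenicity data might explain the Visit 2 item. That is possible, and nothing is claimed here about that sample. The SAP does not give this reason, however, and it places exploratory endpoints elsewhere.

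Thirdly, the protocol's summary of changes (1.3.2) says the set is for subjects who complete procedures as planned, which could include Visit 2. That is a rationale for an amendment. The operative definitions in protocol 13.1.1 and SAP Table 2 require an effect on immunogenicity.

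It is also true that no bias is shown and that the loss of precision is slight.

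**Conclusion.** The point holds and is minor. The Visit 2 half of the SAP 7.1 item does not fit the SAP's definition of a major deviation for the titer analyses, and the SAP 9 reference to Table 1 leaves the same question open. Each subject lost from 80 widens the log-scale interval by about 0.6%. Even 12 lost would widen it by 8.5% and the SRR interval by less than 2 points. These sizes rest on assumed miss counts and assumed SRRs of about 60% and 80%.

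The primary result is not threatened. Immunogenicity is also analysed on the Safety Set, which keeps every vaccinated subject, and SAP 8.1 requires reasons for exclusion to be summarized and listed, so any such loss would be visible.

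**What to change.** For the HBGA-blocking and pan-Ig per-protocol analyses, limit the SAP 7.1 timing item to Visit 3. In SAP 9, reword the exclusion so that it applies to subjects whose Day 29 (Visit 3) samples fall outside the Table 1 window. Keep one base definition of the Per Protocol Set. If the exploratory endpoints need a Visit 2 criterion, state it in the separate exploratory document and apply it only to analyses that use the Day 8 sample.

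The cost is two wording changes before database lock, with no new data. The one downside is that the subjects analysed may differ between the titer analyses and any Day 8 exploratory analysis, so the exploratory document must state its added criterion.

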## 7.2 Subgroups

There will not be any subgroup analysis for this study.

## 7.3 Missing Data

### 7.3.1 Partial Dates/Times

Partial dates and times for AEs, medical conditions, concomitant medications and other vaccinations will be imputed for the purpose of calculating duration. Imputed dates and times should not be shown in the listings.

Partial AE onset, concomitant medication and other vaccinations start dates will be imputed as follows:

- If only the month and year are specified, and the month and year of the trial vaccination is not the same as the month and year of the start date, then use the 1st of the month.
- If only the month and year are specified, then set to the date of the trial vaccine received in the same month and year. If this results in a start date after a known or partial end date, then use the 1st of the month.
- If only the year is specified, and the year of the trial vaccination is not the same as the year of the start date, then use January 1st of the year of the start date.
- If only the year is specified, then set to the date of the trial vaccine received in the same year. If this results in a date that is after the known end date of the AE/medication/other vaccination then use the date of the trial vaccination or January the 1st, whichever is the latest.

If the start date is completely unknown, then use the date of the trial vaccination. If this results in a date that is after the known end date of the AE/medication/other vaccination, do not impute the start date.

Partial AE start times will be imputed as follows:

- If the actual or imputed start date is the same as the date of the trial vaccination and the start time is completely missing, then use the time of the trial vaccination administration.
- If the actual or imputed start date is not the same as the trial vaccine administration, and the start time is completely missing, then use 00:00.
- If the actual or imputed start date is the same as the trial vaccine administration, and the start time is partially missing (hh:XX) then use the following:
  - If the hour is the same as the hour of the trial vaccine administration time then use the complete time of trial vaccine administration (i.e., both hours and minutes).
  - If the hour is not the same as the hour of the start time than use hh:00.
- If the actual or imputed start date is not the same as the trial vaccine administration date, and the start time is partially missing (hh:XX) then use hh:00.

Partial medical conditions start dates will be imputed as follows:

- If only the month and year are specified, then use the 1st day of the month.
- If only the year is specified, then use January 1st of that year.
- If the start date is completely unknown, do not impute the start date.

Partial AE resolution, medical conditions and concomitant medications stop dates will be imputed as follows:

- If the event, condition or medication is flagged as ongoing, do not impute the stop date.
- If only the month and year are specified, then use the last day of the month.
- If only the year is specified, then use December 31st of that year.
- If the stop date is completely unknown, do not impute the stop date.

